11.0 Statistical Analysis

This is a single arm phase II trial. Prior head and neck investigations of IMRT to minimize 3D conformal toxicity have anticipated (and demonstrated) a 30% decrease in symptoms when IMRT is utilized³⁸. Non-randomized analyses have suggested that the benefit of IMRT approaches a 50% decrease in symptoms³⁹. Thus, to be conservative, the null hypothesis of this analysis is that two year VHI scores will be 33% lower than baseline. This represents a decline from an average VHI global score of 44 to about 29, a decline of 15 points. Our alternative of interest is a 50% decline in VHI global score, a decline of 22 points. L. Di Nicola et al (ref) tabulated such scores and we have taken their estimate of the standard deviation at baseline of VHI global score, std = 8.5. We used this same value for the 2 year score, which is not given by Di Nicola, but is close to the 3 year score when VHI scores have further declined. This, in turn, gives the std of baseline less 2 year scores of 8.5 times 1.414. VHI average scores are estimated to be normally distributed.

We will obtain baseline and 2 year VHI scores for an initial cohort of 15 patients. We will terminate the study after the first 15 patients have been evaluated at 2 years if their average decline is less than 15. Otherwise we will recruit an additional 15 patients. If the overall average of all 30 patients is at least 19.2 we will reject the null hypothesis. The design has 50% chance of early stopping under the null and a 2.58% chance of early stopping in error. The overall type I error is 5% and the study power is 85%.

We will test the null hypothesis that at most 85% of patients will achieve local control versus the alternative that at most 95% of them will. If less than 13 of the initial cohort

of 15 experience local control, we will interrupt the study for futility. If at least 28 of 30 acquire local control we will reject the null and declare the local control rate to be 95%. The chance of early stopping for lack of local control is 40% when the true local control rate is 85%. The chance of early stopping in error is 3.6%. The overall power is 81% and overall type I error is 15.1%.

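### The primary VHI decision uses a fixed cut of 19.2 that ignores the SD observed in the trial: the stated 5% type I error holds only at an SD of change near 14.1, and at the plan's own SD of 12.02 it is 2.7%

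*Combined protocol and SAP*

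**What the plan says.** Section 11.0 sets the null for the fall in VHI from baseline to 2 years: "This represents a decline from an average VHI global score of 44 to about 29, a decline of 15 points". The target is larger: "Our alternative of interest is a 50% decline in VHI global score, a decline of 22 points". The first 15 patients are evaluated at 2 years, and the trial stops if their mean decline is below 15. Otherwise 15 more are recruited, and the final rule is: "If the overall average of all 30 patients is at least 19.2 we will reject the null hypothesis".

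The variability behind that cut is built in three steps. A cited study supplies "the standard deviation at baseline of VHI global score, std = 8.5". For the later time point, "We used this same value for the 2 year score"; the section says that the source does not give the 2-year value, and refers to closeness with the 3-year score. Then: "This, in turn, gives the std of baseline less 2 year scores of 8.5 times 1.414". Normality is assumed: "VHI average scores are estimated to be normally distributed".

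The section claims 50% early stopping under the null, 2.58% early stopping in error, 5% type I error and 85% power. For this decision it describes no test statistic, no confidence interval and no check of the SD against the trial's own data.

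**The concern.** A fixed cut on a mean has its nominal error rate at exactly one SD. Two of the three ingredients of that SD are assumptions: the 2-year SD, and the zero correlation implied by the factor 1.414. When the decision is made, the trial will hold 30 change scores and can estimate the SD directly, but the rule does not use them.

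If the true SD of change is smaller than the one at which the cut gives 5%, the test is stricter than claimed and gives up power. If it is larger, a positive result carries more than the stated false-positive risk. In either case the printed 5% does not describe the test that will be made.

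**Working it through.** **Inputs (all Section 11.0).** Null decline 15; alternative 22; stage 1 n = 15, stop if the mean is below 15; final n = 30, reject if the mean is at least 19.2; both SDs 8.5; SD of change 8.5 × 1.414 = 12.02; normal data.

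**Method.** The first-15 mean and the 30-patient mean are bivariate normal with correlation √(15/30) = 0.707 and standard errors SD/√15 and SD/√30. The chance of rejecting is P(mean of 15 ≥ 15 and mean of 30 ≥ 19.2).

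**Step 1: the plan's own figures at SD 12.02.** The standard errors are 12.02/√15 = 3.104 and 12.02/√30 = 2.195.

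- Early stopping under the null: P(Z < 0) = 50%. This matches the plan, and would do so at any SD.
- Early stopping in error: (15 − 22)/3.104 = −2.255, giving 1.21% (stated 2.58%).
- Type I error: (19.2 − 15)/2.195 = 1.914, a tail of 2.78%; with stage 1 included, 2.74% (stated 5%).
- Power: (22 − 19.2)/2.195 = 1.276, giving 89.9%; with stage 1 included, 89.6% (stated 85%).

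The three stated figures correspond to SDs of about 13.9 (2.58%), 14.1 (5%) and 14.4 (85%). Other readings do not recover them. A t reference distribution gives 3.28% and 89.4%, and a null decline of 14.67 or 14.52 in place of 15 gives a type I error of 1.9% or 1.6%.

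**Step 2: type I error and power of the fixed cut by SD of change.** With both SDs at 8.5 and correlation ρ, the SD of change is 8.5 × √(2(1 − ρ)).

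| SD of change | Basis | Type I error | Power at 22 |
|---|---|---|---|
| 8.5 | both SDs 8.5, ρ = 0.5 assumed | 0.34% | 96.4% |
| 12.02 | the plan (ρ = 0) | 2.74% | 89.6% |
| 16 | sensitivity only | 7.2% | 82.0% |
| 17 | sensitivity only (ρ = −1 with both SDs 8.5) | 8.4% | 80.3% |
| 20 | sensitivity only | 11.7% | 75.7% |

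For any ρ ≥ 0 with both SDs at 8.5, the SD of change is at most 12.02 and the type I error at most 2.7%.

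**Step 3: a test that uses the observed SD.** Keep stage 1. At 30 patients, reject if (mean − 15)/(s/√30) exceeds 1.699 (one-sided 5%, 29 df), where s is the observed SD. Because the stage 1 cut equals the null value, the whole rule is scale-free under the null, so its type I error does not depend on the SD. Simulation puts it at about 4.9% at each SD tried from 8.5 to 20. Power at a 22-point decline is 99.7% (SD 8.5), 92.6% (12.02), 79.6% (15) and 58.4% (20).

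**Step 4: the observed mean then needed, 15 + 1.699 × s/√30.** This is 17.6 at s = 8.5 and 18.7 at s = 12.02. It equals 19.2 at s = 4.2 × √30/1.699, about 13.5.

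**The case against.** The strongest reply is that a pre-stated numerical cut is a transparent go/no-go rule for a small single-arm phase II trial, and that calibrating it at a planning SD is a legitimate design choice. On the plan's own SD the rule errs on the safe side: the true SD could be about 17% above 12.02 (14.1/12.02 = 1.17) before the error passes 5%. That stands, and it limits the point. It does not rescue the printed 5% and 85%, which do not follow from the stated SD.

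Three further replies also have force.

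- Not everything was assumed. The baseline SD comes from a cited study, and the section offers some reason for the 2-year value.
- The rise in power from 89.6% to 92.6% at SD 12.02 is not a merit of the t-test as such. It comes from spending type I error that the 19.2 cut leaves unused. A fixed cut of about 18.6 would hold 5% at SD 12.02 with 93.6% power. What the t-test adds is that the error rate stays put if the SD is something else.
- A fixed 19.2 also acts as a minimum observed effect, 19.2/44 = 44% of the baseline mean. The t-test lowers that bar when scatter is small: 17.6/44 = 40% at an observed SD of 8.5. This matters because the primary endpoint in Section 2 is framed as a 50% improvement.

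A reader might infer from the sensitivity figures that the trial's actual false-positive rate may exceed 10%, or that any scatter wider than planned makes success too easy. The documents support neither. More than 10% needs an SD of change above about 18.4, some 53% over the plan (18.4/12.02 = 1.53). With both SDs at 8.5, even a correlation of −1 gives only 17, and 8.4%.

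**Conclusion.** The point holds in a limited form. The primary decision ignores the observed SD, so its type I error is whatever the true SD of change makes it: 5% only near 14.1, and 2.7% with 89.6% power at the plan's own 12.02. Within the plan's SDs of 8.5 and any non-negative correlation, the rule is needlessly strict, down to 0.3% at an assumed correlation of 0.5; a higher correlation would give less. Error above 5% is a sensitivity result at SDs that the documents do not support, not a finding about this trial.

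These figures rest on normal change scores, all 30 patients having both scores, and a null of exactly 15. The correlation of 0.5 and every SD other than 12.02 are assumptions. This should be changed: it concerns the primary test, and the correction needs no new data.

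**What to change.** Keep the stage 1 rule. Replace the final rule with wording such as: reject the null if a one-sided 5% one-sample t-test of the 30 observed change scores against a decline of 15 is significant, that is, if the lower one-sided 95% confidence limit for the mean decline exceeds 15. Report the mean decline with its confidence interval. Restate the operating characteristics at SD 12.02: just under 5% type I error (about 4.9%), about 92.6% power at a 22-point decline, 50% early stopping under the null and 1.2% early stopping in error.

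The change is to analysis wording only, with no added patients, visits or measurements. It has three costs:

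- The observed mean needed for success is no longer fixed. It falls below 19.2 when scatter is small and rises above it once the observed SD exceeds about 13.5.
- Power still depends on the SD. At SD 20 it would be 58%, against 76% for the fixed cut, which there carries 11.7% type I error.
- The implied minimum observed effect is lost. If the sponsor wants one, it can keep 19.2 as an additional requirement and state the resulting error and power. At SD 12.02 these cannot exceed the fixed cut's own 2.7% and 89.6%.

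### The type I error, power and erroneous-stopping figures stated for the VHI rule in section 11.0 do not follow from the inputs stated there (2.7%, 89.6% and 1.2%, against 5%, 85% and 2.58%).

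*Combined protocol and SAP*

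**What the plan says.** Section 11.0 gives every input needed to check the VHI design.

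- **Null:** "This represents a decline from an average VHI global score of 44 to about 29, a decline of 15 points".
- **Alternative:** "Our alternative of interest is a 50% decline in VHI global score, a decline of 22 points".
- **Variability:** a published baseline SD of 8.5 is also used at 2 years. The cited source gives no 2-year value, and the plan's reason for the choice is that 8.5 "but is close to the 3 year score when VHI scores have further declined". Then: "This, in turn, gives the std of baseline less 2 year scores of 8.5 times 1.414". Normality is assumed.
- **Stage 1:** "We will terminate the study after the first 15 patients have been evaluated at 2 years if their average decline is less than 15". Otherwise 15 more patients are recruited.
- **Final rule:** "If the overall average of all 30 patients is at least 19.2 we will reject the null hypothesis".
- **Claimed properties:** "The design has 50% chance of early stopping under the null and a 2.58% chance of early stopping in error", and "The overall type I error is 5% and the study power is 85" percent.

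**The concern.** The properties of a two-stage rule for a normal mean with a known SD are fully determined by the two means, the SD, the stage sizes and the two boundaries. Section 11.0 states all of these, so its error rates and power should be reproducible. Three of the four are not.

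VHI at 24 months is the primary endpoint, and these figures justify both the sample size and the 19.2 cut-off. If the documented SD is right, the error rates and power are misreported and the cut-off is stricter than a 5% test needs. If the design was calculated with a larger SD, the plan misstates its variance assumption. The text does not let a reader decide between the two.

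**Working it through.** **Inputs (all from section 11.0).** Null mean decline 15; alternative 22; SD of change 8.5 × 1.414 = 12.019; n = 15 at stage 1 and 30 in total; stop if the stage-1 mean is below 15; reject if the mean of 30 is at least 19.2.

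**Standard errors.** SE(15) = 12.019/√15 = 3.103. SE(30) = 12.019/√30 = 2.194. The correlation between the stage-1 mean and the overall mean is √(15/30) = 0.707.

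**Early stopping.** P(stop) = Φ((15 − μ)/3.103).
- μ = 15: Φ(0) = 50.0%, as stated. The boundary equals the null mean, so this holds at any SD and does not confirm the SD used.
- μ = 22: Φ(−7/3.103) = Φ(−2.256) = 1.20%, against the stated 2.58%.

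**Rejection.** P(reject) = P(mean of first 15 ≥ 15 and mean of 30 ≥ 19.2), from the bivariate normal distribution.
- μ = 15: the final cut-off alone gives 1 − Φ(4.2/2.194) = 2.78%. With the interim rule it is 2.74%, against the stated 5%.
- μ = 22: the final cut-off alone gives Φ(2.8/2.194) = 89.9%. With the interim rule it is 89.6%, against the stated 85%.

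A simulation of 4,000,000 trials agrees: 2.76%, 89.65% and 1.21%.

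**Could another convention explain the gap?**

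| Variant | Type I error | Power | Erroneous stopping |
|---|---|---|---|
| Stated in the plan | 5% | 85% | 2.58% |
| Inputs as written | 2.74% | 89.6% | 1.20% |
| Simple t approximation | 3.3% | 89.4% | 2.0% |
| One-sided error doubled | 5.5% | 89.6% | 1.20% |
| Unrounded null decline (14.52 or 14.67) | 1.6% to 1.9% | 89.6% | 1.20% |
| SD 8.5, without the 1.414 factor | 0.34% | 96.4% | 0.07% |
| SD 14 (not in the documents) | 4.9% | 85.7% | 2.64% |
| 11 + 11 patients, SD 12.02 (contrary to the text) | 4.9% | 85.6% | 2.67% |

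No variant that keeps the documented SD and sample sizes gives all three stated figures. An SD near 14 comes close, but no single SD matches all three exactly: 2.58% needs SD 13.93, 5% needs 14.09, and 85% needs 14.37.

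**Comparison with the plan's other rules.** The same kind of calculation for the local-control rule in section 11.0 gives 39.6%, 3.6%, 81.2% and 15.1%, against the stated 40%, 3.6%, 81% and 15.1%. The SAE rule in section 12.0 gives 3.62%, 60.2%, 4.34% and 79.3%, exactly as stated. Only the VHI figures fail.

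**Dependence on the SD.** The final cut-off makes no use of the observed SD, so the properties of the written rule move with the true SD. The factor 1.414 assumes zero correlation between baseline and 2-year scores. The SDs below are assumptions and are not in the documents.

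| Assumed SD of change | Type I error | Power |
|---|---|---|
| 8.5 (per-visit SD 8.5, correlation 0.5) | 0.3% | 96.4% |
| 10.06 (per-visit SD 8.5, correlation 0.3) | 1.1% | 93.6% |
| 14 | 4.9% | 85.7% |
| 16 | 7.2% | 82.0% |
| 20 | 11.7% | 75.7% |

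**Cut-off for a 5% test at SD 12.02.** Solving for the final boundary gives 18.58, with power 93.6%. Rounded to 18.6, it gives 4.9% and 93.5%.

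**The case against.** The strongest reply concerns weight. At the documented SD every discrepancy is favourable: fewer false positives, more power and fewer wrongful stops. No boundary or patient number has to change. If 5% and 85% are read as a ceiling and a floor, the design meets both. The consequence is indeed modest, and that limits how serious the point is. But the section does not present the figures as bounds, and that reading cannot account for a value given to two decimals, 2.58%, which is more than twice the computed one.

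A second reply is that SD 14 and 11 + 11 patients are guesses. That is correct. Neither is in the documents, and 11 + 11 contradicts the stated cohorts. They show only the direction in which an unreported input might lie.

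Third, the zero-correlation assumption is visible in the factor 1.414, and the plan gives a reason for using 8.5 at 2 years. With equal SDs, a positive correlation would make the rule more conservative. Neither choice is an error, though both remain assumptions. With a per-visit SD of 8.5, change SDs of 14 or more would need a negative correlation, so the upper part of the range mainly represents larger per-visit SDs.

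Finally, a cut-off of 18.6 loosens the success criterion. The present 19.2 is 43.6% of the baseline 44, and 18.6 is 42.3%, further from the 50% improvement named as the primary endpoint in section 2.2. This is a fair reason to prefer restating the figures, or disclosing the input, over moving the cut-off.

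**Conclusion.** The concern holds. From the inputs in section 11.0, the VHI rule has a type I error of 2.7% (stated 5%), power of 89.6% (stated 85%) and a 1.2% chance of stopping in error (stated 2.58%). Rounding does not explain the gap. The cause is either wrong stated figures or an input that the plan does not report, and the documents do not say which.

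The result assumes normal change scores, the planned SD of 12.02 treated as known, and evaluable baseline and 2-year scores for all 30 patients; section 11.0 makes no allowance for dropout. On these assumptions the error is conservative and does not leave the trial underpowered. It should be corrected because it misdescribes the primary design, but it does not prevent the rule from being applied.

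**What to change.** Before any 2-year VHI data are seen, reconcile section 11.0 in one of three ways:

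1. Keep the 19.2 cut-off and SD 12.02, and restate the figures as 2.7% type I error, 89.6% power and 1.2% erroneous stopping.
2. If a 5% test is intended at SD 12.02, set the cut-off to about 18.6 and state about 5% type I error and 93.5% power. This changes the success criterion, so it needs an amendment before those data are seen.
3. If a different SD or cohort size was used in the calculation, state and justify it.

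Option 1 or option 3 is enough to remove the error. In each case, say that zero correlation is assumed and add a short sensitivity range for smaller and larger SDs. Options 1 and 2 cost one recalculation and some wording, with no extra patients.

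Separately and optionally, a one-sided 5% one-sample t-test with the observed SD and the same futility rule would hold the type I error near 5% (4.8% to 4.9% in simulation at SDs from 8.5 to 20). Its power is 92.6% at SD 12.02, but it has less power than the fixed cut-off at larger SDs: 75.1% against 82.0% at SD 16, and 58.3% against 75.7% at SD 20.

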2.0 Objectives

To define a new treatment technique for T1a larynx cancer that maintains excellent local control with less extensive radiation fields

Hypothesis: Contralateral arytenoid sparing IMRT for T1a larynx cancer maintains the excellent local control associated with whole larynx radiation and results in functional outcomes at 24 months after therapy that are suggestive of improved function when compared to historical controls

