12.0 Data and Safety Monitoring Plan

This is a deintensification study – patients will be receiving a smaller field of radiation to the same dose as standard therapy.

Therefore, this study is felt to represent a minimal risk to patient safety outside of the primary endpoint.

Even though the investigational treatment is the same dose as prescribed in the standard of care but to a smaller volume, unknown factors relating to toxicity will not be discounted. We accept the possibility of at most 5% SAEs among our patients and will consider the treatment too toxic if a 20% SAE rate is encountered.

If 3 patients have a SAE within the first cohort of 15 treatments, the trial will be terminated.

If 5 patients among the 30 experience a DLT the treatment will be considered too toxic and will not be pursued further. The chance of early termination if the SAE rate is 5% is 3.62% and the rate of early termination when the true SAE rate is 20% is 60.2%.

The overall chance of declaring the treatment too toxic in error is 4.34% and this chance when the true toxic rate is 20% is 79.3%.

Per standard institutional protocol, patients will have acute toxicity monitored at least weekly using CTCAE v4.0.

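### The stated powers and false-stop chances each hold for one rule on its own, but any of three rules can halt the trial at 15 patients, and no figures are given with all three in force

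*Combined protocol and SAP*

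**What the plan says.** Three rules act on the first 15 patients.

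- **VHI (section 11.0).** The study terminates if the mean fall at two years is below 15 points. Otherwise 15 more patients are recruited, and the null is rejected if the mean fall in all 30 is at least 19.2. Early stopping is put at 50% under the null and 2.58% in error. Then: "The overall type I error is 5% and the study power is 85" per cent.
- **Local control (section 11.0).** If fewer than 13 "of 15 experience local control, we will interrupt the study for futility". The null is rejected with at least 28 of 30 controlled. The chance of stopping in error is 3.6%, and "The overall power is 81% and overall type I error is 15.1" per cent.
- **Toxicity (section 12.0).** "If 3 patients have a SAE within the first cohort of 15 treatments, the trial will be terminated". The chance of this at a 5% SAE rate is 3.62%.

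The VHI planning values are a null fall of 15 ("This represents a decline from an average VHI global score of 44 to about 29, a decline of 15 points"), an alternative of 22 ("Our alternative of interest is a 50% decline in VHI global score, a decline of 22 points"), and an SD for the change that "gives the std of baseline less 2 year scores of 8.5 times 1.414".

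Neither section gives a figure for the three rules acting together, or says that a stop under one rule leaves the other tests running.

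**The concern.** A stop under any one rule leaves 15 patients, so neither 30-patient test can be carried out. A power that allows for only one of the three stops is therefore higher than the design delivers when all three apply. The same holds for the false-stop chances: three figures of about 3% each do not tell the reader how likely it is that a technique meeting every planning value is halted at 15. Anyone judging the design, or interpreting a trial that stopped, would rely on these figures. Section 11.0 also calls the 85% the study power, which invites reading it as a property of the whole design.

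**Working it through.** **Inputs.** All are from sections 11.0 and 12.0: falls of 15 and 22; SD of change 8.5 × 1.414 = 12.02; VHI cut-offs 15 (n = 15) and 19.2 (n = 30); local control 85% and 95%, with cut-offs 13 of 15 and 28 of 30; SAE stop at 3 of 15. Two assumptions are mine: the three outcomes are independent, and the SAE rate lies between 0 and 5%. Section 12.0 treats 5% as the most it will accept.

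**Step 1: each rule alone.**

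*Local control at 95%.*
- P(X ≤ 12 of 15) = 3.62% (stated 3.6%).
- P(X ≥ 28 of 30) = 81.2% (stated 81%). The rule's own early look costs nothing here: 28 of 30 allows at most two failures, so the first 15 must contain at least 13 successes.
- At 85%, early stopping is 39.6% and type I error 15.14% (stated 40% and 15.1%). All four figures reproduce.

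*SAE at 5%.* P(X ≥ 3 of 15) = 3.62%, as stated.

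*VHI at SD 12.02.*
- The standard error is 12.02/√15 = 3.10 at 15 patients and 12.02/√30 = 2.19 at 30. The two means have correlation √(15/30) = 0.707.
- False stop: Φ((15 − 22)/3.10) = Φ(−2.26) = 1.2% (stated 2.58%).
- Power, from the bivariate normal: 89.6% (stated 85%).
- Type I error: 2.7% (stated 5%).
- Only the 50% stop under the null reproduces. The stated 2.58% would need an SD of about 13.93, which gives about 4.8% type I error and 85.9% power.

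**Step 2: all three rules in force.** Multiply each test's own power by the chance of passing the other two rules at 15 patients. At a 5% SAE rate and SD 12.02:

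- VHI: 0.896 × 0.9638 × 0.9638 = 83.3%
- Local control: 0.812 × 0.988 × 0.9638 = 77.3%
- Any false stop at 15: 1 − 0.988 × 0.9638 × 0.9638 = 8.2%
- Both tests succeed: 0.896 × 0.812 × 0.9638 = 70.2%

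With no SAEs the last factor drops out of the local control, false-stop and both-succeed products, and one of the two 0.9638 factors drops out of the VHI product.

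| Basis | SAE rate | VHI power | Local control power | False stop at 15 | Both succeed |
|---|---|---|---|---|---|
| SD 12.02 | 5% | 83.3% | 77.3% | 8.2% | 70.2% |
| SD 12.02 | 3.5% | 85.2% | 79.1% | 6.1% | 71.8% |
| SD 12.02 | 0% | 86.4% | 80.2% | 4.8% | 72.8% |
| Stated 85% and 2.58% | 5% | 79.0% | 76.3% | 9.5% | 66.5% |
| Stated 85% and 2.58% | 0% | 81.9% | 79.1% | 6.1% | 69.0% |
| Stated in the plan | – | 85% | 81% | 2.58%, 3.6%, 3.62% separately | not given |

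**Step 3: dependence.** In a simulation at SD 12.02 and a 5% SAE rate, with a latent correlation of 0.3 to 0.6 between favourable outcomes, VHI power was 84–85%, local control 78% and both 71–73%. Positive correlation reduces the loss but does not remove it.

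**The case against.** The strongest reply is that nothing here is miscalculated for local control or toxicity. Those figures reproduce exactly as properties of single rules, and each is printed beside its own rule. That stands: the gap is in labelling and in the missing combined figures.

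The reply also has force for VHI. The 5% SAE rate is a ceiling, and at SD 12.02 VHI power with all three rules in force is still 85.2% at a 3.5% SAE rate and 86.4% with none. It falls below the stated 85% only near the ceiling, and then by about 2 points.

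A reader might infer that the design really delivers 79% for VHI and 66% for the two tests together, so that one trial in three fails even if every assumption is true. The documents do not support this. The 79%, the 66% and the 9.5% false stop start from the stated 85% and 2.58%, which do not follow from the plan's SD and cut-offs. Nor do the documents define success as both results. The hypothesis in section 2.0 joins them ("maintains the excellent local control associated with whole larynx radiation and results in functional outcomes at 24 months"), and section 2.1 lists both as primary objectives. But section 2.2 names VHI as the primary endpoint and lists local control as secondary, and section 11.0 sets out two separate tests. The chance that both succeed is useful background, not a stated power that has been missed.

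A further argument is that local control power falls to about 39% when VHI sits at its null (0.812 × 0.5 × 0.9638). That is a futility stop doing its job and adds nothing to the point.

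Finally, section 11.0 says interrupt for local control but terminate for VHI. If only a pause is meant, VHI power rises (0.896 × 0.9638 = 86.4% at a 5% SAE rate). Local control power stays at 77.3%, because three failures in the first 15 already rule out 28 of 30.

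**Conclusion.** The point holds as one of incomplete and unlabelled operating characteristics.

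- **Local control** is the firm part. The stated 81% is for that rule alone. With all three rules it is about 77% at a 5% SAE rate and 80% with no SAEs, a loss of about 1 to 4 points.
- **VHI** loses about 3 to 6 points against its own stand-alone 89.6%, giving 83% to 86%. The result straddles the stated 85%, so a shortfall against that figure is not established.
- **False stop at 15** is about 5% to 8%, against separately quoted values of 2.58%, 3.6% and 3.62%.

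These values assume a true fall of 22, local control of 95%, independence, SD 12.02, and that each stop ends the whole trial. On the stated VHI figures instead, at a 5% SAE rate, they become 76%, 79% and 9.5%. The chance that both tests succeed is about 70–73% (66–69% on the stated VHI figures) and is supplementary only.

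The separate mismatch between the VHI figures and SD 12.02 is the larger numerical fault in the quoted sentence, and it has to be settled before any combined VHI figure can be printed.

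**What to change.** 1. In section 11.0, reconcile the VHI type I error (5%), power (85%) and false-stop chance (2.58%) with the stated SD and cut-offs, correcting whichever is wrong.
2. In sections 11.0 and 12.0, label every power and false-stop figure as holding if no other rule stops the trial, and do not describe 85% as the power of the study.
3. Add a short table of VHI power, local control power and false stop at 15 with all three rules in force, for SAE rates from 0 to 5%. State the independence assumption. The chance that both tests succeed can be included if marked as supplementary.
4. Say whether a local control interruption ends the trial or pauses it.

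This changes wording and one small table only. No patients are added, and no stopping rule or cut-off needs to change for this point. The cost is a slightly less favourable stated power. The combined figures should not be copied from the stated 85% and 2.58% before step 1 is done.

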2.2.2 Secondary Endpoints

Demonstrate a similar 2-yr local control of (>85%) with IMRT therapy for T1a and T2aN0 larynx cancer

Evaluate clinician-reported voice quality at defined intervals up to 24 months after the completion of radiation using the Grade, Roughness, Breathiness, Asthenia, and Strain (GRBAS) scale

Use the Eating Assessment Tool (EAT-10) to evaluate patient-reported satisfaction with swallowing at up to 24 months after the completion of radiation

Evaluate clinician-reported measures of swallowing 24 months after the completion of radiation as measured by fiberoptic endoscopic evaluation of swallowing (FEES) using the penetration, aspiration scale (PAS) scores for 3 commonly evaluated textures (cookie, puree, thin).

2.3 Purpose/Specific Aim of this Research Study: To define a new treatment technique for T1a larynx cancer that maintains excellent local control with less extensive radiation fields

2.4 Hypothesis: Contralateral arytenoid sparing IMRT for T1a larynx cancer maintains the excellent local control associated with whole larynx radiation and results in functional outcomes at 24 months after therapy that are suggestive of improved function when compared to historical controls

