6.0 Risks to Participants

Limited field radiation may not be as successful as whole larynx RT and there may be an increased risk of treatment failure

It is unknown if unilateral radiation introduces asymmetric function in the larynx. However, single vocal cord targeted therapy (surgery) causes no noticeable asymmetric symptoms³ (reduced comfort and exacerbated throat clearing), so the risk is anticipated to be small

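### Section 11.0 would declare local control to be 95% after 28 of 30 successes, but the test supports only a rate above 85%, and even 30 of 30 would not establish 95% at the plan's own error level.

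*Combined protocol and SAP*

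**What the plan says.** Section 11.0 (Statistical Analysis) sets the hypotheses this way: "We will test the null hypothesis that at most 85% of patients will achieve local control versus the alternative that at most 95% of them". There is one interim look: with fewer than 13 successes among the first 15 patients, the study is interrupted for futility. The final rule is: "If at least 28 of 30 acquire local control we will reject the null and declare the local control rate to be 95" per cent. The section gives the chance of early stopping as 40% when the true rate is 85% and 3.6% when stopping would be an error, and then: "The overall power is 81% and overall type I error is 15.1" per cent.

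Section 2.1 lists two-year local control among the primary objectives. Section 2.2.2 lists it as a secondary endpoint, with a more modest target: "Demonstrate a similar 2-yr local control of (>85%) with IMRT therapy for T1a and T2aN0 larynx cancer". No confidence interval or other estimate of the local control rate is specified anywhere.

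**The concern.** A test that rejects a rate of 85% or less permits the conclusion that the rate is above 85%, at the test's error level. It does not show that the rate equals the design alternative. The plan nevertheless attaches a specific rate of 95% to any result at or beyond the boundary.

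The stated alternative does not help. As worded ("versus the alternative that at most 95% of them will"), it covers every rate up to 95%, including every rate in the null, so it does not define what is concluded on rejection.

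What is at stake is the claim the trial may make about the main efficacy risk of a smaller field. Section 6.0 acknowledges it: "Limited field radiation may not be as successful as whole larynx RT and there may be an increased risk of treatment failure". A report that followed section 11.0 literally would state 95% control when the observed rate might be 93.3% and the data were compatible with a considerably lower rate. With no interval planned, nothing in the document would temper that statement.

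**Working it through.** **Inputs (all from section 11.0).** Null rate 0.85; design alternative 0.95; stop if fewer than 13 of the first 15 have local control; reject if at least 28 of 30 do.

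**1. Reproduce the stated design.** X1 is the number of successes in the first 15 patients and X the number in all 30. At least 28 of 30 means at most 2 failures, so a passing result always has at least 13 of the first 15. Hence P(X1 ≥ 13 and X ≥ 28) = P(X ≥ 28), and single-stage exact limits apply unchanged.

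P(X ≥ 28) = 435·p^28·(1−p)^2 + 30·p^29·(1−p) + p^30

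- p = 0.85: 0.1034 + 0.0404 + 0.0076 = 0.1514
- p = 0.95: 0.2586 + 0.3389 + 0.2146 = 0.8122

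| Quantity | Stated | Recomputed |
|---|---|---|
| Early stop, P(X1 ≤ 12), at 0.85 | 40% | 39.6% |
| Early stop, P(X1 ≤ 12), at 0.95 | 3.6% | 3.62% |
| Type I error | 15.1% | 15.14% |
| Power at 0.95 | 81% | 81.2% |

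All four reproduce. The 15.1% type I error is disclosed and is not itself an error.

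**2. What each passing result supports.** The limits are exact (Clopper-Pearson). The one-sided lower limit at level α solves P(X ≥ x | p) = α. For 28/30 at α = 0.1514 it is 0.85 by construction. For 30/30 it is 0.1514^(1/30) = 0.939.

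| Result | Observed | Exact two-sided 95% CI | One-sided lower limit, α = 15.14% | One-sided lower limit, α = 5% |
|---|---|---|---|---|
| 28/30 | 93.3% | 77.9% to 99.2% | 85.0% | 80.5% |
| 29/30 | 96.7% | 82.8% to 99.9% | 89.2% | 85.1% |
| 30/30 | 100% | 88.4% to 100% | 93.9% | 90.5% |

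No lower limit reaches 95%.

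**3. At what level could 30/30 establish 95%?** P(30/30 | p = 0.95) = 0.95^30 = 21.5%. A perfect result therefore cannot exclude a rate of 95% or less at any one-sided level below 21.5%. With no failures at all, excluding it would take ln(0.151)/ln(0.95) = 36.9, so 37 patients, at the 15.1% level, or ln(0.05)/ln(0.95) = 58.4, so 59 patients, at the 5% level.

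**4. How often the rule, and so the 95% statement, would be triggered.**

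| True local control | P(at least 28 of 30) |
|---|---|
| 88% | 28.5% |
| 90% | 41.1% |
| 92% | 56.5% |
| 95% | 81.2% |

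These are ceilings, because the VHI interim rule (section 11.0) and the SAE rule (section 12.0) can also end the study at 15 patients.

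**The case against.** The strongest defence is that this is a two-point decision rule, with 85% and 95% as design points and an error rate at each. In that setting, naming the alternative on rejection is familiar shorthand for acting on it, and the stated power shows that 95% was the design point. Section 2.2.2 already gives the target as above 85%. At true rates of 88%, 90% or 92% the null is false, so rejecting it is the right decision and only the label is wrong. The value 95% also lies inside all three exact 95% intervals.

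Much of this stands. The figures in step 4 are probabilities of a wrong label, not of a wrong decision, and 95% is compatible with every passing result. The statement that no result could establish 95% also needs a level: it holds at 15.1%, 5% and 2.5%, and would fail only above a one-sided 21.5%.

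It does not rescue the sentence. Being compatible with 95% is not the same as showing it, the text names a specific rate as the conclusion, and the miswritten alternative offers no better reading. Nothing elsewhere in the document corrects it.

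A second objection is that a conclusion of above 85% at 28/30 would sit beside a 95% interval that includes 85% (77.9% to 99.2%). That is true. The two use different levels, and stating the 15.1% level explicitly makes the difference visible.

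**Conclusion.** The concern holds. The boundary and its operating characteristics are correct, but the conclusion attached to them is not supported by any passing result at the plan's own 15.1% level, where the lower limits run from 85.0% (28/30) to 93.9% (30/30). At the boundary the plan would declare a rate 1.7 percentage points above the one observed (95.0 − 93.3). The declaration also goes beyond the endpoint of above 85% in section 2.2.2, which the test can support.

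This rests on exact binomial calculation with 30 evaluable patients, and on reading the final rule as written. It should be fixed because it governs what the trial may claim on a stated primary objective. It does not invalidate the design.

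**What to change.** In section 11.0, remove the statement that the rate will be declared to be 95%, correct the alternative, and replace both with wording such as:

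> The null hypothesis that local control is at most 85% is tested against the alternative that it is greater than 85%, with power computed at 95%. If at least 28 of 30 patients have local control at 2 years, the null is rejected at a one-sided level of 15.1% and local control is concluded to exceed 85%. The observed rate is reported with its exact 95% confidence interval.

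Reporting the one-sided lower limit at the 15.1% level as well (85.0% at 28/30) would show directly how the test and the wider 95% interval fit together.

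The cost is wording only. The interim and final boundaries, sample size, type I error and power are unchanged. The price is a less favourable claim: above 85% instead of 95%.
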